## 9. RESEARCH METHODS

### 9.1 STUDY DESIGN

The SITS-IVT>80 years is an observational, multinational, multicenter study in patients with acute ischaemic stroke treated with IV thrombolysis according to SmPC. This is a retrospective study based on existing data collected in the registry for patients treated according to the revised and approved Summary of Product Characteristics (SmPC) of IVT>80 years in European countries.

Approximately 1000 patients older than 80 years treated with IV Alteplase are expected to be identified for the proposed SITS-IVT>80 year study in the post-approval period of 3 years (1 July 2018 to 30 June 2021) and also approximately 1000 patients above 80 years treated with IV Alteplase within 4.5 hours otherwise according to SmPC in the pre-approval period (June 2015 to June 2018). Of these, at least 500 patients each should be registered from European centers (see list of European countries being part of the mutual recognition procedure) during the pre-approval as well as in the post-approval period. If the target 1000 patient is not reached during the 3 year period (post-approval phase), the data exchange will stop provided at least 500 patients registered from European centers have been included into the analysis.

The aim is to investigate the incidence rate of SICH, death and functional independence (mRS) / favorable outcome (primary endpoints) at day 90 in post-approval registered group of >80 year old patients and to compare with pre-approval registered group of >80 year old patients, comparison will be in both unmatched and the propensity score matched groups in the SITS-ISTR registry.

Additional analyses will be made with regards to patient's characteristics, management time (secondary endpoints): onset of symptoms to time of treatment initiation, and its components: onset of symptoms to door; door to treatment initiation.

### 9.2 SETTING

The SITS-IVT>80 years Study is driven by the SITS International according to SITS policy, and data will be provided to the Regulatory Authorities as needed. Acute ischaemic stroke patients aged >80 years who received IV thrombolysis according to SmPC during the period June 2015 to June 2021 were considered. Of these, pre-approval sample will consist at least 1000 patients from June 2015 to June 2018 and post-approval sample of 1000 patients from July 2018 to June 2021.

#### 9.2.1 Level of care

- Thrombolysis treatment should be given at a semi-intensive care unit within a stroke unit, or an intensive care unit or semi-intensive care unit in close collaboration with the stroke unit, under the responsibility of an experienced stroke neurologist/stroke

physician. This stroke neurologist/stroke physician should have personal experience from thrombolysis treatment in stroke.

#### Inclusion criteria

- Patients over 80 years old presenting with acute ischaemic stroke symptoms for which thrombolysis treatment was initiated within 4.5 hours after stroke onset according to SmPC are included.
- Patients over 80 years who received thrombolysis according to SmPC for AIS within 4.5 hours after stroke onset during the period (approximately 3 years) prior to July 2018 are included.

#### Exclusion criteria

- Contraindication(s) to the use of IV thrombolysis per local SmPC.
- Documentation that the patient was enrolled or is planned to be enrolled in an investigational clinical trial at the time of the onset of index event and for the duration of the data collection.

## 9.3 VARIABLES

### 9.3.1 Exposures

#### Intravenous thrombolysis

Index date is defined as the date of initiation of IV thrombolysis with alteplase (Actilyse®).

Intravenous thrombolysis with tissue plasminogen activator (tPA) within 4.5 hours of ischaemic stroke onset is an established and approved treatment. The effect of iv thrombolysis is time-dependent. Among patients treated within one hour, every second patient is expected to fully recover within three months, among those treated within 90 minutes, every third, and within 3 hours every seventh patient. For patients treated within the time interval of 3-4.5 hours, 14 patients need to be treated for one additional patient to recover fully. IV thrombolysis given within three hours from stroke onset increases the chance of reaching good functional outcome (defined as having exactly the same functional level as before the stroke) from 23% to 33%, and when given between 3 and 4.5 hours from onset, by a more modest but still substantial absolute 5%. The use of iv thrombolysis is increasing but still used in only 10-15% of all ischaemic stroke patients. Meanwhile, 2-7% of patients treated with iv thrombolysis suffer symptomatic intracerebral haemorrhage (ICH) as a complication, leading to death in 1.5-2%, and worsening functional outcome in survivors.

Administration of plasminogen activator as an intravenous infusion is thus a method to enhance this endogenous procedure. Reperfusion should of course be done as early as possible to avoid a cerebral lesion, and to avoid complications caused by ischaemic injury to blood vessel walls and the blood-brain barrier.

Treatment with Actilyse must be started as early as possible within 4.5 hours of the onset of symptoms. Beyond 4.5 hours after onset of stroke symptoms there is a negative benefit risk ratio associated with Actilyse administration and so it should not be administered.

The recommended total dose is 0.9 mg alteplase/kg body weight (maximum of 90 mg) starting with 10% of the total dose as an initial intravenous bolus, immediately followed by the remainder of the total dose infused intravenously over 60 minutes.

Patients in general will be exposed once to Actilyse for the treatment of the acute ischemic index event.

### 9.3.2 Outcomes

#### 9.3.2.1 Primary outcomes

##### Primary outcome

- Safety: SICH per SITS-MOST definition
- Mortality (mRS=6) within 90 days
- Outcome: Functional Independence as defined by mRS 0-2 within 90 days

A modified Rankin score, mRS, is used to evaluate daily activity of the patient at day 90 (described in Attachment 8.3). The scores are entered in the on-line entry form. The score 0-1 is defined as favourable outcome and 0-2 as independence of the patient.

Symptomatic intracerebral haemorrhage, SICH, is defined as 'Intracerebral haemorrhage' (parenchymatous haemorrhage type 2, PH2), at the 22-36 hours post-treatment scan combined with neurological deterioration leading to an increase of 4 points on the NIH Stroke Scale' (SITS-MOST definition).

The evaluation of post-treatment haemorrhage is done using the CT/MRI scan performed between 22-36 hours after start of treatment or earlier if clinically indicated.

Death within 90 days as classified by the investigator according to cause: cerebral infarct, cerebral haemorrhage, cerebral infarct and haemorrhage unspecified, myocardial infarct, pulmonary embolism, pneumonia, other vascular cause, unknown and other cause of death (ICD 10 to be provided).

#### 9.3.2.2 Secondary outcomes

##### Secondary outcomes

- Patient characteristics at baseline including stroke severity (NIHSS)
  - Outcomes: Favourable outcome as defined by mRS 0-1 within 90 days
  - Secondary safety: SICH per ECASS 2 within 90 days
  - Delays of management
    - Time from onset of symptoms – start of treatment
    - Time from onset of symptoms – door (or as captured in the registry arrival at hospital)
    - Door – needle time

### **9.3.3 Covariates**

#### **Specification of data collection from the index stroke event**

At baseline: Demographic data (age, sex, weight), NIHSS and pre-stroke mRS, blood pressure, laboratory values (plasma glucose, cholesterol) medical history including comorbidities and concomitant medication, results of imaging scans, time logistics

At 24 hours: NIHSS score, blood pressure, laboratory and imaging scans if performed.  
During hospital stay: details of concomitant medications, additional imaging scans

At 7 day or discharge if occurred earlier than 7 days: Date/time discharge, NIHSS scores, blood pressure, type of stroke and AF, medications

At 3-months follow up: mRS scale, any events including recurrent stroke (haemorrhagic or ischaemic), major extracranial haemorrhage

The analysis will include standard covariates.

Standard SITS-ISTR safety parameters:

- Baseline and demographic variables available in SITS for describing patient characteristics such as but not limited to stroke severity, age, gender etc. (standard covariates)

- Symptomatic intracerebral haemorrhage (SICH):

Intracerebral haemorrhage (parenchymatous haemorrhage type 2), at post-treatment scan combined with neurological deterioration leading to an increase of 4 points on the NIH Stroke Scale (SITS-MOST definition)

- Mortality:

Death (mRS = 6) at day 90

- Independence / favourable outcome:

Independence for the activities of daily living at day 90. Good functional outcome is defined as a modified Rankin Scale (mRS) score of both 0-2 (independence) and 0-1 (favourable) and independency / favourable outcome at 90 days (mRS 0-2, mRS 0-1)

Patient management variables

- o Time from onset to door
- o Door to needle (treatment) time

Onset to treatment time

## **9.4 ONSET TO TREATMENT TIME DATA SOURCES**

**Data is collected within the SITS-ISTR registry according to their standard procedures.**

SITS is an academic-driven, non-profit, international collaboration. It is an initiative by the medical profession aimed at driving excellence in acute and secondary stroke treatment, and to develop new knowledge and leading research. SITS-ISTR is an ongoing, prospective, multinational and academic driven registry for centres using thrombolysis for the treatment of acute ischaemic stroke patients. The registry contains data about alteplase treatment independent of the time since stroke onset. Information related to patient demographics, baseline characteristics, stroke severity at baseline, onset to treatment time, risk factors, drug treatment history, admission time and data on baseline and follow-up imaging scans are collected in SITS-ISTR

## **9.5 STUDY SIZE**

The sample size was not based on any formal power calculation, rather chosen pragmatically in consultation with authorities and based on numbers achievable within a 3-year period. Approximately 2000 acute ischaemic patients who were treated with IV thrombolysis within 4.5 hours within symptom onset constitute the main analysis population. Data from a minimum of 500 European patients are expected within the database during post approval phase as well as equal number during the pre-approval phase in patients > 80 years old acute ischemic stroke patients.

## **9.6 DATA MANAGEMENT**

Data in the SITS registry are entered on-line through the SITS website. SITS uses the two-factors authentication to login to the registry, i.e. first by username and password and then by a code which is sent to the user either by SMS or by e-mail. Each investigator/study nurse has a personal access code which must be kept secret and used only by the owner. All data entry from a centre can be made by each member of the local team, but once the data entry is confirmed (i.e. cannot be changed), the person who made the confirmation will be identified on the data entry form.

For the purpose of analysis, a download will be made in Excel/ CSV format which will then be transferred in the appropriate advance data analysis software such as STATISTICA/ SAS.

Data collection in this study is approved as part of the SITS-ISTR study framework by the Regional Research Ethics Committee in Stockholm, Sweden. Data analyses are performed according to SITS policy and under the responsibility of the Scientific Committee.

## **9.7 DATA ANALYSIS**

A non-interventional post-approval study on SITS-ISTR existing data of intravenous rt-PA (0.9 mg/kg) in acute ischaemic stroke patients over 80 years, according to the Summary of

Product Characteristics (SmPC) of European countries being part of the mutual recognition procedure within the academic SITS-ISTR (International Stroke Thrombolysis Registry, ongoing since December 2002).

Descriptive statistics (absolute and relative frequencies, means, standard deviations, medians, inter quartile ranges, minimum and maximum values, 95% confidence intervals and proportions, as appropriate) for baseline and demographic characteristics for all included patients will be provided. To compare demographic and clinical baseline characteristics between pre-approval and post-approval patients over >80 years, standardized differences will be used. Multivariable analyses (exploratory) with adjustment for differences or imbalances in prognostic variables for outcome comparison will be performed.

### 9.7.1 Main analysis

We will compare the outcome of interest both in unmatched and propensity score matched patient sets as described below. The primary analysis will be on propensity score matched patient sets and we will compare the post-approval >80 year old patients with the pre-approval retrospective >80 year olds regarding baseline demographics, clinical and radiological parameters, as well as treatment logistics, safety outcomes, functional outcome and death. Secondary analysis will be on unmatched patient sets, i.e. all patients fulfilling the inclusions-exclusions criteria will be included in this analysis. A sensitivity analysis restricted to European and non-European patients might be considered if minimum sample size required for analysis is met in the matched patient set.

Patient sets analysed includes “unmatched” and “matched”. “Unmatched” patients set composed of IV thrombolysis treated patients >80 years from both pre-approval and post-approval phase those who fulfil the inclusions-exclusions criteria. Matched patient set constitute propensity score matched pair (1:1 greedy nearest neighbour matching using calipers equal to 0.2\*SD of the logit of the propensity score).

The incidence rate and corresponding 95% CI of patients with primary and secondary outcome events will be calculated within the following cohorts:

- a) Patients >80 years after approval
- b) Patients >80 years before approval

The incidence rate for the outcome of interest using as-treated approach will be calculated on the unmatched (all eligible patients) and the matched patient sets.

In the primary analysis, post-approval >80 year old patients will be matched to pre-approval >80 year old patients using a structured, iterative propensity score model with the primary objective to maximize the balance in the distribution of possible confounders between these two groups [9].

In the propensity score-matching algorithm, all baseline characteristics will be included. The corresponding propensity score of the post-approval >80 years group will be calculated for

each subject and a nearest neighbour matching algorithm will then be used to match patients in the post-approval >80 years group to patients in the pre-approval >80 years group within 0.2\*SD of the logit of the propensity score. To determine whether the propensity score approach achieved balance in all potential confounders, we will compare all baseline characteristics of patients in the post-approval >80 years group to their propensity score matched pre-approval >80 year old patients using standardized difference.

We will also compare baseline characteristics between the unmatched and propensity matched subgroups to detect potential imbalances between the two populations. Differences of outcome between post-approval >80 years and pre-approval >80 years will be evaluated with univariable and multivariable binary logistic regression models adjusting for potential confounders. In these models the factors that contribute to the outcome of interest in the initial univariable analyses at p values <0.1, will be included in the multivariable model as candidate variables. The final variables that will be independently associated in the multivariable logistic regression analyses with the outcome of interest will be selected by backward stepwise selection procedures using a p value <0.05.

## 9.8        **QUALITY CONTROL**

European Stroke Centres (approx. 60) continuously registering patients into SITS-ISTR having

- a typical experience from acute stroke treatment
- high quality (at least 90% complete data entered at acute phase and 70% data entered at 3m follow up) in both prospective and retrospective groups
- a willingness to participate in SITS-IVT>80 years registry

### 9.8.1        **Investigators and local procedures**

According to the current processes in SITS described on the SITS web site ([www.sitsinternational.org](http://www.sitsinternational.org)) the following persons are involved;

#### National Coordinator

A National Coordinator (NC) is appointed by SITS as to be the responsible person for the SITS activity in the specific country. The NC has an overview of the infrastructure in regards to stroke care treatments in the country. The role of NC is to coordinate among the different centers in the country. SITS has engaged leading stroke scientists as National Coordinators in each participating country.

#### Local coordinator/ Centre coordinator

The Local Coordinator (LC) is responsible for the centre activity and ultimate responsibility of the data entered in the SITS registry from the hospital. The LC must be a doctor authorised by the medical head of the department.

**Local user**

The Local User (LU) is responsible for entering data in the SITS registry. The LU must be appointed by the LC and operating within the stroke unit.

Internal data quality controls will be done by the SITS Coordinating Office, which will include:

1. Validation rules for key data parameters so that impossible data will not be possible to enter
2. Online monitoring to find out inconsistent data entry, data completeness
3. In addition to online data monitoring, inconsistency and completeness check every 6 months. Normally investigators are informed by newsletter regarding the completeness of data entry for overall registry and asked to complete the missing data. In case of major inconsistency or high rate of missing data investigators are contacted personally by e-mail.

## **9.9 LIMITATIONS OF THE RESEARCH METHODS**

### **Non-interventional study based on existing data**

The quality of a study based on existing data relies on accuracy of recorded data. Important data may not be available.

#### **Selection bias**

There is a risk of selection bias at the patient level. Sites might preferentially include "interesting" cases to the SITS study. To minimize selection bias at the patient level, centres were reminded by e-mail every 3 months that all consecutive patients from each site who meet entry criteria must be included in the SITS-Registry.

#### **Lost to follow up**

As with all observational studies a loss to follow up can occur. In this study this will affect the patients with a pre-planned follow up (patients initiating IV thrombolysis within the 3 months after the index event). However, considering the short time period of the follow up and the lost to follow up at 3 months in the general SITS Registry being 20%, a similar percentage of lost to follow up is expected in this study as well.

For the analysis of clinical outcome events we do not exclude patients lost to follow-up after IV thrombolysis initiation and before the 3 months after index event, which could lead to underidentification of clinical outcome events.

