What is the aim of the analyses: To show, if there are differences between pre- and post-approval populations in the safety, outcomes and in the baseline parameters?

Can differences in the outcomes be explained by differences in the baseline parameters?

Primary analyses: Propensity score matching should diminish differences in the outcomes if patients have balanced baseline parameters. If differences persist or an improvement or worsening of outcomes in the post approval phase occurs, other explanations are needed (as processes in the hospital (shorter or longer of door to needle time or increase of experience). This might need further exploration

Secondary analyses:

To confirm the results of the PS matching by adjusting the model parameter “post-approval vs pre-approval patient” for the most important imbalanced confounders for the outcomes of interest.

Descriptive statistics (absolute and relative frequencies for categorical variables, means, standard deviations, medians, inter quartile ranges, minimum and maximum for continuous/ordinal variables) for baseline, demographic characteristics and outcomes for all included patients will be provided separately for pre-approval and post-approval patients. In addition, 95% Wald confidence intervals will be provided for the continuous outcomes and Wilson score interval with continuity correction for binary outcomes. To compare difference among demographic and clinical baseline characteristics between pre-approval and post-approval, standardized differences will be used. Propensity score matching will be the primary statistical approach, multivariable modeling will be used for secondary complementary explorative analysis.

Primary Analysis

The primary analysis will be on propensity score matched patient datasets and we will compare the post-approval with the pre-approval patients regarding baseline demographics, clinical and radiological parameters, as well as treatment logistics, safety outcomes, functional outcome, and death.

Matched patient set constitute propensity score matched pair (1:1 greedy nearest neighbor matching using calipers equal to $0.2 \times \text{SD}$ of the logit of the propensity score)¹. The primary propensity score will be based on the variables listed below. These variables were selected based on established clinical significance and relevant SmPC criteria available in the SITS database.

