Age, sex, pre-stroke Modified Rankin Scale (mRS) score, baseline NIHSS score, systolic blood pressure and glucose level, antiplatelet treatment at stroke onset, history of hypertension, diabetes, atrial fibrillation, hyperlipidaemia, smoking and previous stroke earlier than 3 months, stroke onset to IVT treatment start time. We will include a baseline covariate only if 85% of the patients have a value reported.

A sensitivity PSM analysis will also be performed based on all baseline characteristics among patients with complete information. To determine whether the propensity score approach achieved balance in all potential confounders, we will compare all baseline characteristics of patients in the post-approval group to their propensity score matched pre-approval patients using standardized difference. If standardized difference >0.2 then propensity score model will be modified with inclusion of interactions and variable transformations to achieve better balance.

Relative risks for binary and mean difference for continuous/ordinal primary and secondary outcomes in post-approval vs pre-approval will be calculated together with 95% profile likelihood confidence intervals and likelihood ratio test p-values for relative risks and 95% Wald confidence intervals and Wald test p-values for mean differences.

Secondary Analysis

Secondary analysis will be on all patients fulfilling the inclusions-exclusions criteria.

Relative risks and mean difference for secondary outcomes in post-approval vs pre-approval will be calculated together with 95% confidence intervals and p-values.

Outcomes among post-approval vs pre-approval will be evaluated with generalized linear multivariable regressions with appropriate response distribution depending on outcome adjusting for potential confounders. Link function will be chosen as to estimate relative risks for binary outcomes and difference for continuous outcomes.

For each primary and secondary outcome covariates in models will be chosen according to the following:

- 1) Factors that contribute to the outcome of interest in an initial univariable analyses at p values <0.1 and variables known to influence outcomes such as age, sex, baseline NIHSS score and pre-stroke mRS, will be included in the multivariable model as candidate variables.
- 2) Final variables among the candidate variables with the outcome of interest will be selected by backward stepwise selection procedures using a p value <0.05 .

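### Patients lost before 90 days stay in the outcome analysis with no value assigned, which biases the absolute 90-day rates of independence and death downward

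*Protocol*

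**What the plan says.** Protocol section 9.9 (Lost to follow up) bases its expectation on "the lost to follow up at 3 months in the general SITS Registry being 20" per cent and anticipates a similar figure here. It then says: "For the analysis of clinical outcome events we do not exclude patients lost to follow-up after IV thrombolysis initiation and before the 3 months", and adds "which could lead to underidentification of clinical outcome events". Protocol section 9.7.1 says that incidences "will be calculated on the unmatched (all eligible patients) and the matched patient sets".

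The SAP mentions loss to follow-up only as a limitation in section 5 and does not carry over the rule that lost patients are kept. Under Planned Analysis, descriptive "outcomes for all included patients will be provided separately for pre-approval and post-approval patients", with a "Wilson score interval with continuity correction for binary outcomes". Under Primary Analysis, the comparison uses "95% profile likelihood confidence intervals and likelihood ratio test p-values for relative risks". No denominator is given for those relative risks and no rule for a missing outcome.

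The missing-data rules that do exist concern other things:

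- SAP section 4.2 excludes patients with missing SmPC criteria.
- SAP Primary Analysis admits a baseline covariate only if 85% of patients have a value, and adds a sensitivity matching among patients with complete baseline information.
- Protocol section 9.8 and SAP section 4.1.2 select centres with at least 70% of 3-month data entered.
- The ENCePP checklist, item 10.7, answers Yes on missing-data methods and points to section 9.8, which holds completeness thresholds, entry checks and reminders but no analytic method.

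**The concern.** Independence (mRS 0-2) and death within 90 days are two of the three primary outcomes, and reporting their incidence with a 95% CI is a stated aim of the study. A patient who is kept in the denominator, and for whom nothing is recorded at 90 days, adds to neither numerator. The same patient is then treated as alive for one primary outcome and as not independent for the other. Both rates are pushed down, and the confidence interval, computed as if every status were known, does not show it.

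The SAP does not repair this. Because it names neither a value for a missing mRS nor a denominator for the relative risks, the choice could be made after the data are seen.

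**Working it through.** The documents state no 90-day rates and no power calculation, so there is no planned figure to reproduce. The check asks what the rule does to a plausible rate.

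**Inputs from the documents.** Expected loss L = 20% (Protocol 9.9). Group size about 1000 per period, with a floor of 500 from European centres (Protocol 9.1, 9.5). Wilson interval with continuity correction (SAP Planned Analysis).

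**Assumptions, not in the documents.** True independence p = 35%. True death d = 20-30%. Share of deaths already recorded by discharge or 7 days, f = 0 or 0.5. L = 10% as a lower value, because the 70% centre rule could bring loss below the registry average. L = 30% as the upper value, the most that rule allows in any one centre.

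**Independence.** Let k be the independence rate in lost patients divided by the rate in followed patients. With lost patients kept as non-events:

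reported rate = p(1 - L) / [(1 - L) + kL]

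For loss unrelated to outcome (k = 1) this is p(1 - L):

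- L = 10%: 0.35 x 0.90 = 31.5%
- L = 20%: 0.35 x 0.80 = 28.0%
- L = 30%: 0.35 x 0.70 = 24.5%

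At L = 20% with other loss mechanisms:

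- k = 0: 0.28 / 0.80 = 35%, no bias
- k = 0.5: 0.28 / 0.90 = 31.1%
- k = 1.5: 0.28 / 1.10 = 25.5%

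Only k = 0, where no lost patient was independent, removes the bias.

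**Coverage.** This is the exact binomial probability that the planned interval contains the true 35%:

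| Loss | k | Reported | Coverage, n = 1000 | Coverage, n = 500 |
|---|---|---|---|---|
| 10% | 1 | 31.5% | 38% | 65% |
| 20% | 0.5 | 31.1% | 28% | 58% |
| 20% | 1 | 28.0% | 0.3% | 9% |
| 20% | 1.5 | 25.5% | <0.1% | 0.4% |

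For a reported 28% at n = 1000 the interval is 25.3-30.9%.

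**Death.** Deaths recorded early still count, and loss of 20% applies to everyone else:

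reported rate = d[f + (1 - f)(1 - L)]

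- f = 0: 0.80d, so 20-30% is reported as 16-24%
- f = 0.5: 0.90d, so 20-30% is reported as 18-27%

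**Relative risk.** With loss unrelated to outcome, the independence relative risk is multiplied by (1 - L post) / (1 - L pre). Equal loss gives a factor of 1. As an illustration of unequal loss only, 20% before and 30% after approval would give 0.70 / 0.80 = 0.875 when the true relative risk is 1.

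**SICH per SITS-MOST.** It is determined by the scan at 22-36 hours (or earlier) and early neurological change, so 3-month loss hardly touches it.

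**The case against.** The strongest reply has four parts.

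**The coding is inferred.** Section 9.9 gives no outcome value, and its sentence can be read as a rule about who belongs to the cohort. A descriptive table for all included patients can also show a row of missing values. This stands as a caution: non-event coding is an inference. It is nevertheless the natural one, because keeping patients in the denominator with no event recorded is how events come to be under-identified.

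**A denominator is given.** A reader might infer that none is stated anywhere. The documents do not support that: section 9.7.1 gives one for incidences. What is missing is the value for a lost patient and the denominator of the SAP relative risks. A reader might also infer that the SAP's incidences and relative risks rest on different patients. That is possible but not written; the text is silent rather than contradictory.

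**The comparison is largely spared.** The primary analysis is the matched post/pre contrast, and equal loss cancels from the relative risk. A reader might infer that the contrast itself is biased, but no text suggests that loss differs between periods. This part stands in full.

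**The size depends on assumptions.** The bias varies with the loss mechanism and with the amount of loss. At 10% loss, coverage at 1000 per period is 38% rather than 0.3%. This also stands, which is why a range is shown. Neither end of it is acceptable for a nominal 95% interval.

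Both documents disclose under-identification, and the protocol abstract calls its analyses descriptive and exploratory. Disclosure does not correct a primary incidence, nor does it tell the programmer what to do.

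**Conclusion.** The point holds for the absolute 90-day incidences and should be fixed. Followed as written, keeping lost patients among all eligible patients under-reports independence unless no lost patient was independent, and under-reports death by less when early deaths have been recorded.

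With an assumed true independence of 35% and loss unrelated to outcome, the shortfall is 7 points at 20% loss (35 - 28) and 3.5 points at 10% loss (35 - 31.5). Coverage falls to about 0.3% and 38% respectively at 1000 per period. These figures rest on assumed event rates and on reading a retained patient without data as a non-event.

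The finding does not extend to the post/pre relative risk unless loss, or its relation to outcome, differs between periods, nor to SICH per SITS-MOST.

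**What to change.** Replace the retention sentence in Protocol section 9.9 and add a matching rule to the SAP under Planned Analysis:

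1. Count any death recorded up to day 90, at any visit, as dead and not independent.
2. Treat every other missing 90-day mRS as missing, not as a non-event. Handle it by multiple imputation within period, using age, pre-stroke mRS, NIHSS at baseline, 24 hours and 7 days, and discharge mRS. All of these are listed in SAP Appendix 1. Use the same denominator for incidences and relative risks in each patient set.
3. Report completeness of 3-month status by period, with sensitivity analyses on observed mRS only and under best and worst cases. Completeness by period will also show whether the relative risk needs attention.

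The cost is a short amendment to both documents and modest programming, with no new data collection. Intervals become slightly wider, and results depend on the imputation model; the sensitivity analyses make that dependence visible.
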